1. Pregnant women in the EXE group gain less weight than those in the MOT group
2. Pregnant women in the MOT group gain less weight than those in the CON group.

Exploratory outcomes

- Complementary data on levels of physical activity are determined using doubly labeled water, questionnaires, and additional data from the activity tracker.
- Clinical and metabolic health parameters in mother and offspring.

Section 3: Study Methods

Trial design

Single-site three-armed randomized controlled trial.

Brief description of the interventions

The targeted physical activity level for all participants in the EXE and MOT groups is at least 30 minutes per day at moderate intensity as recommended to healthy pregnant women [6].

Standard care control group (CON)

The CON group is offered standard care at the hospital.

Structured supervised exercise training (EXE)

The training is performed in groups and supervised by health professionals. It consists of three weekly one-hour exercise sessions at a moderate intensity, including two land exercise sessions and one water exercise session.

Motivational counseling supported by health technology (MOT)

This intervention comprises four individual and three group counseling sessions during the pregnancy as well as weekly SMS-reminders. The overall focus of both the individual and group counseling sessions is to create a climate that taps into what already motivates the participants to increase or maintain their physical activity level. The activity trackers are used as an intervention element to motivate the participants to increase their physical activity levels. The weekly SMS-reminders have supportive and motivating content and are used to encourage the participants to achieve a moderate physical activity level.

Changes of the intervention during the COVID-19 pandemic

During the COVID-19 pandemic, EXE is converted to exercise at home with online group sessions. MOT is also held online. As much data as possible will be collected during the pandemic, but some clinical data may not be possible to obtain.

Randomization

After a one-week baseline period where the physical activity level is measured by the activity trackers, the women are randomly assigned in a 1:2:2 ratio to CON, EXE or MOT. The randomization is performed via a numbered randomization list administered through the electronic database REDCap and the investigators are blinded to the randomization procedure.

Sample size

[figure not shown]
Primary outcome

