The expected lost-to-follow-up rate needs to be considered and added to the sample size. Therefore, we will include 44 participants in CON and 88 participants in EXE and MOT, respectively, in total 220 women, based on an expected lost-to-follow-up rate of 20%, as seen in similar exercise studies in pregnant women [6,10,12,19]. This should leave 35 participants in CON (0.8×44) and 70 participants in each of the two intervention groups (0.8×88), which will give sufficient power for analysis of the primary outcome.

Secondary outcome

Based on a comparable intervention study with exercise training [21], the estimated GWG in the intervention and control groups had standard deviations of 4 kg. Thus, in the present study, 33 women in the CON and 66 in each of the intervention groups (EXE and MOT) are needed to detect a difference of 2.8 kg between the control and the intervention groups with a power of 0.80 and two-sided α -level of

0.05. The sample size calculation to this secondary outcome was performed during the intervention but before the intervention was completed.

Framework

The hypothesis testing framework is based on model comparisons using the Likelihood Ratio Test of equality between null and alternative models.

Statistical interim analyses

No interim analyses will be performed. The trial will not be stopped early as a result of data analyses.

Timing of final analysis

The final analysis of the primary outcome will be performed when the last participant has passed GA week 28+6. The final analysis of the secondary outcome will be performed when the last participant gives birth.

Timing of outcome assessments

The primary outcome is measured continuously (24/7) from randomization to GA week 28+6. The secondary outcome is measured at baseline (max. GA week 15+0), GA week 28+0-6, GA week 34+0-6 and at delivery.

Section 4: Statistical Principles

Confidence intervals and P values

The level of statistical significance is 5%. The primary analysis containing two hypotheses will be tested at a significance level of 2.5% each to control the family-wise type I error. Wald-based 95% confidence intervals will be given for all reported estimates.

Adherence, protocol deviations, and analysis populations

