Number of participants	N=220
Age (years)	Mean ± (SD) or median (IQR)
Weight (kg)	Mean ± (SD) or median (IQR)
BMI at inclusion (kg/m ²)	Mean ± (SD) or median (IQR)
Gestational age at inclusion (weeks)	Mean ± (SD) or median (IQR)
Education level (1-3)	n/Total (%)

The number of babies (no.)	Mean ± (SD) or median (IQR)
Marital status (married or have partner/not)	n/Total (%)
Alcohol consumption before pregnancy (serving/week)	Mean ± (SD) or median (IQR)
Alcohol consumption during pregnancy (serving/week)	Mean ± (SD) or median (IQR)
Smoking status (current smoker)	n/Total (%)
Employed (yes/no)	n/Total (%)
Physical activity at work (active/sedentary)	n/Total (%)
Fertility treatment (no.)	n/Total (%)
Self-reported weekly physical activity level during pregnancy before inclusion (≤30 minutes or 30-60 minutes)	n/Total (%)
Minor health problems (no.)	n/Total (%)
Pelvic pain during pregnancy (yes/no)	n/Total (%)
Pelvic pain before pregnancy (yes/no)	n/Total (%)
Total cholesterol (mmol/L)	Mean ± (SD) or median (IQR)
HDL (mmol/L)	Mean ± (SD) or median (IQR)
LDL (mmol/L)	Mean ± (SD) or median (IQR)
HbA1c (mmol/mol)	Mean ± (SD) or median (IQR)
Triglycerides (mmol/L)	Mean ± (SD) or median (IQR)
Steps per day (average steps/day)	Mean ± (SD) or median (IQR)
Active calories (calories/day)	Mean ± (SD) or median (IQR)
Moderate to vigorous physical activity (minutes/week)	Mean ± (SD) or median (IQR)
Active time (minutes/day)	Mean ± (SD) or median (IQR)
Floors walked (no./week)	Mean ± (SD) or median (IQR)
Minimum heart rate (beats/min)	Mean ± (SD) or median (IQR)
Average heart rate (beats/min)	Mean ± (SD) or median (IQR)
Maximum heart rate (beats/min)	Mean ± (SD) or median (IQR)
Resting heart rate (beats/min)	Mean ± (SD) or median (IQR)
Metabolic equivalent of task (MET/day)	Mean ± (SD) or median (IQR)
Move IQ (%type of physical activity)	Mean ± (SD) or median (IQR)

Section 6: Analysis

Outcome definitions

Primary outcome

The primary outcome, MVPA, is measured continuously (24/7) by an activity tracker and will be presented in minutes per week from randomization to GA week 28+6.

Secondary outcome

The secondary outcome is GWG, i.e. weight gained from the onset of the pregnancy to giving birth. GWG is determined as the difference between body weight on the day of birth and preconception body weight.

All other outcomes will not be presented with hypothesis testing, and they will be represented as exploratory outcomes.

Analysis methods

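### The gestational weight gain sample size does not follow from its stated inputs: at 1:2 allocation, 25 vs 50 women give 80% power, and the stated 33 vs 66 give about 90%

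*SAP*

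**What the plan says.** The SAP's Sample size section (Section 3), under Secondary outcome, takes an SD of 4 kg for GWG in both intervention and control groups from a comparable exercise trial. It concludes that "33 women in the CON and 66 in each of the intervention groups (EXE and MOT) are needed". The target, between control and intervention, is 2.8 kg, at power 0.80 and two-sided alpha 0.05. For this calculation it names no test, multiplicity adjustment or dropout allowance.

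Four other places bear on the sentence:

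- **Randomization (Section 3):** "the women are randomly assigned in a 1:2:2 ratio to CON, EXE or MOT". The figures 33, 66 and 66 are in that same ratio.
- **Secondary objective (Section 2):** two GWG hypotheses. The first is "Pregnant women in the EXE group gain less weight than those in the MOT group"; the second compares MOT with CON.
- **Confidence intervals and P values (Section 4):** the general level is 5%. The only split is for the primary outcome: "The primary analysis containing two hypotheses will be tested at a significance level of 2.5% each to control the family-wise type I error".
- **Outcome definitions (Section 6):** after defining the primary outcome and GWG, the SAP says "All other outcomes will not be presented with hypothesis testing". GWG is therefore formally tested.

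**The concern.** The sentence gives every input needed for a two-group comparison of means, yet those inputs do not return its result. The gap between 33 and 25 in the control group is too large to come from rounding or from using a normal rather than a t calculation.

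What is at stake is the meaning of the stated alpha and power for an outcome that will be tested. If the calculation used a split alpha, the sizing and the Section 4 testing rule disagree. If it used 5% per contrast, either the number or the power is wrong. If 0.80 is joint power over two contrasts, the sentence does not say so.

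**Working it through.** **Inputs.** Difference d = 2.8 kg, SD s = 4 kg, power 0.80 (z = 0.8416) and two-sided alpha 0.05 (z = 1.9600), all from the Secondary outcome paragraph. Allocation is 1:2 for CON against one intervention arm, from Randomization.

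**Number needed at 1:2.** n_CON = (1 + 1/2) × (s × (z_alpha + z_power) / d)² = 1.5 × (4 × 2.8016 / 2.8)² = 1.5 × 16.02 = 24.03, rounded up to 25 vs 50. With the noncentral t, 24 vs 48 gives 0.789 and 25 vs 50 gives 0.805, so 25 vs 50 is confirmed.

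**Power of the stated numbers.** SE = 4 × √(1/33 + 1/66) = 0.853 kg, and 2.8 / 0.853 = 3.283. Normal power = Φ(3.283 − 1.960) = 0.907; noncentral t gives 0.902. The difference detectable with 80% power at 33 vs 66 is 2.41 kg (t).

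**Other readings of the sentence.**

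| Reading | Result |
|---|---|
| CON vs both arms pooled, 33 vs 132, 5% | power 0.947 |
| Three-group F test, CON 2.8 kg above both arms, 33/66/66, 5% | power 0.901 |
| Both contrasts with CON significant, 5% each, 33/66/66 | joint power about 0.85 |
| Both contrasts with CON significant, 2.5% each, 33/66/66 | joint power about 0.77 |
| One contrast at 2.5% (the primary-outcome split), 33 vs 66 | power 0.841; 30 vs 60 would suffice |

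None of these gives 0.80 at the stated sizes.

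**Routes that do return 33.**

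| Route | Check | Input not stated for GWG, or contradicted |
|---|---|---|
| Equal allocation, 5% | 2 × 16.02 = 32.04, rounded up to 33; t power at 33 vs 33 is 0.7997 | contradicts 1:2:2 |
| Alpha 0.05/3 per contrast at 1:2 | normal formula 32.05, rounded up to 33; t power at 33 vs 66 is 0.7997, or 0.805 with variance pooled over three groups | three contrasts; the SAP lists two hypotheses |
| Joint power for two 2.8 kg steps (CON to MOT, MOT to EXE), 2.5% each | simulation: 0.806 at 33/66/66, 0.788 at 32/64/64 | the second step, the split and the joint power |
| Power 0.90 at 1:2, 5% | 33 by the normal formula and by t | contradicts power 0.80 |

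Inflating 25 vs 50 for 20% dropout comes close but misses: 25 / 0.8 = 31.25, rounded up to 32, and 50 / 0.8 = 62.5, rounded up to 63.

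**EXE vs MOT.** The sentence does not cover the first GWG hypothesis. At 66 vs 66 the difference detectable with 80% power is 1.97 kg at 5%, 2.17 kg at 2.5% and 2.28 kg at 0.05/3.

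**The case against.** The strongest case on the other side is that this makes almost no difference. On the stated inputs the trial has more power than claimed. Enrolment comes from the primary outcome, and the SAP says the GWG calculation was made while the intervention was under way, so it set no recruitment target. The sentence may also be incomplete rather than miscalculated. The primary outcome was sized for a double hypothesis with a Bonferroni correction, the two GWG hypotheses have the same form, and a joint calculation of that kind does return 33. Finally, Section 4 read plainly has each GWG contrast tested at 5%, so the analysis itself is not ambiguous.

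Most of this stands as a limit on weight. The consequence is small, and which calculation was used cannot be known from the document. The plain reading of Section 4 is also fair, but under it the stated number and power disagree. The joint-power explanation does not rescue the sentence, which gives one difference, between control and intervention, and no EXE–MOT step.

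Two side points need care. Having 33/66/66 with a weight at delivery requires 33/44 = 66/88 = 75% retention. The SAP assumes 80% for the primary outcome, and for the pandemic it warns that "some clinical data may not be possible to obtain". This matters only if 33/66/66 is really needed; if 25 vs 50 suffice, 25/44 = 57% is enough. The EXE–MOT figures are a useful clarification and do not show an error.

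**Conclusion.** The concern holds. With the inputs as written and 1:2 allocation, the number needed for 80% power is 25 vs 50, and the stated 33 vs 66 give 0.90. Nothing else in the SAP supplies an input that reconciles the two. This rests on a two-group comparison of means with common SD 4 kg and two-sided 5% per contrast, as the sentence reads.

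The error is conservative on that reading. The 35/70/70 completers expected for the primary outcome also exceed 33/66/66, if that retention carries over to weight at delivery, which the SAP does not show. This is a sentence that should be corrected; it is not evidence of an underpowered comparison.

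**What to change.** Restate the sentence according to what was actually done:

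- **If 5% applies per contrast:** say that 33 vs 66 women give about 90% power for 2.8 kg (80% for about 2.4 kg), SD 4 kg, two-sided 5% per contrast. Alternatively, give 25 vs 50 as the number needed for 80%.
- **If alpha was split:** keep 33/66/66, state the alpha per contrast (for example 0.05/3), name the contrasts it covers, and apply the same alpha in the GWG analysis.
- **If 0.80 is joint power:** say so, and give both assumed differences and the alpha split.
- **If equal allocation was used:** recalculate at 1:2 and restate as in the first case.

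It would also help to add the difference detectable for EXE vs MOT at 66 vs 66 with 80% power: about 2.0 kg at 5%, 2.2 kg at 2.5% or 2.3 kg at 0.05/3.

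The cost is one sentence in the SAP, with no change to enrolment.

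### The gestational weight gain (GWG) power statement is for control versus the intervention groups, but the GWG hypotheses are EXE versus MOT and MOT versus CON, so the stated 80% does not describe the first hypothesis or, as worded, the pair

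*SAP*

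**What the plan says.** SAP Section 2, secondary objective, lists two GWG hypotheses: "Pregnant women in the EXE group gain less weight than those in the MOT group" and "Pregnant women in the MOT group gain less weight than those in the CON group". Together they state an ordering, EXE below MOT below CON.

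SAP Section 3, Sample size, Secondary outcome, takes from a comparable exercise study that "the estimated GWG in the intervention and control groups had standard deviations of 4 kg". It then puts the requirement at 33 CON women and 66 per programme, which it describes as the numbers "needed to detect a difference of 2.8 kg between the control and the intervention groups with a power of 0.80", at a two-sided alpha of 0.05. It names one difference, between control and intervention. It gives no EXE-MOT difference, no division of alpha between the two GWG hypotheses, and no statement on whether the power is for one hypothesis or for both.

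The primary outcome, with the same pair of contrasts, is treated differently. Its sample size stipulates a separate mean for each group (60, 210 and 150 min/week for CON, EXE and MOT), includes the difference between the two programmes in a double hypothesis, and applies a Bonferroni correction. The significance rule in Section 4 reads "The primary analysis containing two hypotheses will be tested at a significance level of 2.5% each to control the family-wise type I error". No such rule is given for GWG.

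**The concern.** A power figure belongs to a particular contrast at a particular assumed difference. The GWG figure is for control against intervention, while the first GWG hypothesis compares the two programmes with each other. On the plain reading, with both programmes 2.8 kg below control, the planning scenario makes that hypothesis false.

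Section 6 limits hypothesis testing to the primary and secondary outcomes, so GWG is one of only two outcomes formally tested, and the comparison of EXE with MOT is the trial's stated novelty. A reader who meets a power of 0.80 beside these hypotheses will assume that it covers both. A non-significant EXE-MOT difference in GWG could then be taken to mean that the programmes do equally well, although the plan assumed no size for that step.

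**Working it through.** **Inputs from the SAP.** SD 4 kg; difference 2.8 kg between control and intervention; power 0.80; two-sided alpha 0.05; 33 CON, 66 EXE, 66 MOT. Allocation: "the women are randomly assigned in a 1:2:2 ratio to CON, EXE or MOT". The EXE-MOT difference is not stated, so a range is shown.

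**1. The stated figure.** By the normal approximation with k intervention women per control woman, n(CON) = (1 + 1/k) × (1.960 + 0.842)² × (4/2.8)².
- k = 2: 1.5 × 7.85 × 2.041 = 24.0, or 24.7 by the t-test. That is 25 CON and 50 per programme.
- k = 1: 2 × 7.85 × 2.041 = 32.0, or 33.0 by the t-test. That is 33 per group.

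So 33 matches a 1:1 two-group calculation, with 66 as its double. The SAP does not say that it was obtained this way.

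**2. MOT versus CON (hypothesis 2).** SE = 4 × √(1/33 + 1/66) = 0.853 kg. At 2.8 kg, 2.8/0.853 = 3.28, and power = Φ(3.28 − 1.96) = 0.91, or 0.90 by the t-test. At a two-sided alpha of 2.5% the t-test gives 0.84.

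**3. EXE versus MOT (hypothesis 1).** SE = 4 × √(2/66) = 0.696 kg. Power by the t-test:

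| Assumed EXE-MOT difference | alpha 5% | alpha 2.5% |
|---|---|---|
| 1.0 kg | 0.30 | 0.21 |
| 1.4 kg | 0.51 | 0.40 |
| 2.0 kg | 0.81 | 0.73 |
| 2.8 kg | 0.98 | 0.96 |

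With both programmes 2.8 kg below CON the difference is 0, and a significant result in the hypothesised direction has a probability of 2.5% at two-sided 5%.

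**4. Differences detectable with 80% power, per contrast (t-test).**
- At 5%: EXE-MOT 1.97 kg, MOT-CON 2.41 kg.
- At 2.5%: EXE-MOT 2.17 kg, MOT-CON 2.66 kg.

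**5. Both hypotheses together.** The two estimates share the MOT group, so their covariance is −16/66 and their correlation is −0.242/(0.696 × 0.853) = −0.41. The chance that both are significant in the hypothesised direction, by simulation with a pooled SD:

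| EXE-MOT | MOT-CON | alpha for each | both shown |
|---|---|---|---|
| 1.4 kg | 1.4 kg | 5% | 0.13 |
| 1.4 kg | 2.8 kg | 5% | 0.44 |
| 2.0 kg | 2.8 kg | 5% | 0.72 |
| 2.8 kg | 2.8 kg | 5% | 0.88 |
| 2.8 kg | 2.8 kg | 2.5% | 0.81 |

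The first row shares a 2.8 kg EXE-CON difference equally between the two steps. That split is an illustration and is not in the SAP. At the 5% detectable differences in step 4, each contrast has 80% power, but both are shown only about 63% of the time (normal approximation; 62% by simulation).

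**The case against.** The strongest objection is that one scenario does make the 80% a joint figure. If both steps are 2.8 kg and each is tested at 2.5%, as for the primary outcome, joint power is 0.79 with 32 CON women and 0.81 with 33, so 33/66/66 is the first size in that ratio to pass 80%. This shows that the authors may have had a joint calculation in mind. It does not rescue the text. The scenario needs EXE to lie 5.6 kg below CON and needs an alpha split for GWG. The sample-size paragraph states neither, and its single control-intervention difference of 2.8 kg conflicts with the first. A simple 1:1 calculation also gives 33, so the match does not settle the intent.

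Two further objections stand. Hypothesis 2 is a control-intervention contrast and is covered, so it would be wrong to say that neither hypothesis has the stated power. And a reader might infer from the mismatch that hypothesis 1 is underpowered. The SAP does not support that, because power depends on a difference it never states and would be 98% at 2.8 kg.

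It is also fair that enrolment of 220 was set by the primary outcome, that the GWG calculation was made while the intervention was running, and that 95% confidence intervals are planned for all estimates. These points limit the practical harm but leave the statement attached to the wrong contrast.

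**Conclusion.** The concern holds in a limited form. The stated 80% is not the power for EXE versus MOT and, as worded, not the power for the two GWG hypotheses together. For MOT versus CON the stated contrast applies, and 33:66 gives about 90% at two-sided 5% rather than 80%.

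Whether the EXE-MOT comparison is adequately powered cannot be decided from the SAP. At 66 per group and two-sided 5%, power reaches 80% at 1.97 kg and is about 51% at 1.4 kg. The low joint figure of 0.13 rests on an equal split chosen for illustration and should not be reported as the trial's power.

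All figures assume SD 4 kg, 33/66/66 women analysed, and simple comparisons of means without baseline adjustment.

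**What to change.** Restate the GWG power for the two listed contrasts. Give the assumed EXE-MOT and MOT-CON differences, the alpha for each, and whether the power is per hypothesis or joint. The alpha is for the authors to decide, since the SAP sets no split for GWG. Possible wording:

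*With 33/66/66 women and SD 4 kg, the difference detectable with 80% power per contrast is 1.97 kg (EXE-MOT) and 2.41 kg (MOT-CON) at two-sided 5%, or 2.17 and 2.66 kg at 2.5%; the chance of showing both at the 5% values is about 63%. A non-significant EXE-MOT result on GWG is not evidence of equal effect.*

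If a joint calculation with both steps at 2.8 kg was intended, the SAP should say so and state the 5.6 kg EXE-CON difference that it implies.

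The cost is SAP wording only, with no change in enrolment. The downside is that the stated power for the secondary outcome becomes less favourable.

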The treatment effects for the primary and secondary outcomes will be presented as mean differences between the treatment groups adjusted for physical activity at baseline. These values will be estimated from a multiple linear regression model. Analysis of the primary outcome based on multiple imputed datasets will be performed as a sensitivity analysis. The imputations will be performed using the R package “mice” [24]. 25 imputed data sets will be generated using the seed 24658. The imputations will be constructed on the following baseline covariates (body weight, age, group allocation, physical activity at baseline, socio-economic status). In addition, a sensitivity analysis will be performed to investigate whether the COVID-19 pandemic had an impact in the three study groups.

Missing data

The primary outcome will be measured by the activity tracker continuously (24/7) during the intervention. Possible missing data from the tracker due to not wearing the device or other reasons (e.g. skin rash) will be handled according to the predefined inclusion of the data in the analysis. For the primary outcome, a week will be included in the analysis if the week has four or more days with complete data. A day that has six hours or more of non-wear time will be excluded and considered a missing day.

Additional analyses

Analyses describing associations between the level of physical activity, as measured by the activity tracker, and the secondary and exploratory outcomes in all three groups will be performed.

Harms

Information about adverse events (AEs) and serious adverse events (SAEs) will be registered and reported. The AEs/SAEs will be reported as frequency and percentage in the trial groups.

Statistical software

The statistical analysis will be performed using the latest version of R [24].

References

- [2] World Health Organisation (WHO). *Good Maternal Nutrition. The best start in life.* 2016.

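### The weights scheduled at GA 28 and GA 34 for gestational weight gain are not used in its analysis, and nothing is planned for a missing birth-day weight

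*SAP*

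**What the plan says.** Four parts of the SAP bear on this.

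- **Schedule** (Section 3, Timing of outcome assessments): "The secondary outcome is measured at baseline (max. GA week 15+0), GA week 28+0-6, GA week 34+0-6 and at delivery".
- **Definition** (Section 6, Outcome definitions): "GWG is determined as the difference between body weight on the day of birth and preconception body weight". Only two weights enter, and neither is the GA 28 or the GA 34 weight.
- **Analysis** (Section 6, Analysis methods): primary and secondary effects are both given as "mean differences between the treatment groups adjusted for physical activity at baseline". The model is named next: "These values will be estimated from a multiple linear regression model".
- **Missing data** (Section 6, Analysis methods and Missing data): "Analysis of the primary outcome based on multiple imputed datasets will be performed as a sensitivity analysis". The imputation model uses "baseline covariates (body weight, age, group allocation, physical activity at baseline, socio-economic status", so no weight from later pregnancy is in it. The only inclusion rule concerns tracker wear: "For the primary outcome, a week will be included in the analysis if the week has four or more days with complete data".

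Intention-to-treat is stated in Section 4 for the primary analysis. On the pandemic, Section 3 warns that "some clinical data may not be possible to obtain".

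**The concern.** GWG is the only secondary outcome and, apart from the primary outcome, the only one to be tested. The schedule collects two post-randomisation weights for it, and the analysis section gives them no role. A linear regression on a single end-of-pregnancy difference omits any woman whose difference cannot be formed, and the SAP names no substitute weight, imputation or repeated-measures model for GWG. A woman weighed at baseline, GA 28 and GA 34 but not on the day of birth would therefore contribute nothing, although most of her gain is known.

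Two things are at stake. The first is some loss of precision. The second is possible bias if having a birth-day weight depends on earlier gain differently in different arms. Nothing planned for GWG would show whether that had happened.

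**Working it through.** **Inputs from the SAP** (Section 3, Sample size): SD of GWG 4 kg; target difference 2.8 kg; power 0.80; two-sided 5%; 33 women in CON and 66 in each intervention arm required; 44 and 88 randomised; expected loss 20%.

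**Assumptions not in the SAP:**
- the 20% loss rate is also the share m of women lacking a birth-day weight;
- the correlation r between gain to GA 34 and gain to birth is 0.8–0.95;
- a fraction f of the women without a birth-day weight do have a GA 34 weight.

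**The plan's own figure.** With equal arms, n per arm = 2 × (1.960 + 0.842)² × 4² / 2.8² = 32.04, rounded up to 33. Doubling gives 66. At the stated 5% level, 33/66 is thus the 1:1 figure doubled; the 1:2 formula would need only 25/50. The stated size is conservative, with power of 0.907 at 33/66 for one intervention arm against CON.

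**Is the stated size still met?** At 20% missing, 0.8 × 44 = 35.2 and 0.8 × 88 = 70.4 remain, above 33/66. The limit is 33/44 = 0.75, so the requirement fails only when more than 25% of GWG values are missing. Complete-case power for 2.8 kg is 0.966 with none missing, 0.924 at 20%, 0.887 at 30% and 0.836 at 40%.

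**Precision recovered from the earlier weights.** Relative to full data, the variance of an arm mean is 1/(1 − m) for complete cases, which is 1/0.8 = 1.25. Using the GA 34 weights it is (1 − r²)/(1 − m) + r²/(1 − m + mf). With m = 0.2:

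| f | r | Relative variance | SE ratio to complete cases |
|---|---|---|---|
| 1 | 0.80 | 0.36/0.8 + 0.64 = 1.090 | √(1.090/1.25) = 0.934 |
| 1 | 0.90 | 0.19/0.8 + 0.81 = 1.048 | 0.915 |
| 1 | 0.95 | 0.0975/0.8 + 0.9025 = 1.024 | 0.905 |
| 0.5 | 0.80 | 0.36/0.8 + 0.64/0.9 = 1.161 | 0.964 |
| 0.5 | 0.95 | 0.0975/0.8 + 0.9025/0.9 = 1.125 | 0.949 |

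The standard error falls by about 7–10% if all of these women have a GA 34 weight and by about 4–5% if half do. In the half case, the effective CON size rises from 35.2 to 37.9–39.1 and power from 0.924 to 0.940–0.947. At 40% missing with f = 0.5, power rises from 0.836 to 0.893–0.916.

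**Bias from selective missingness in one arm.** Let women above the mean gain at GA 34 be twice as likely to lack a birth-day weight, with 20% missing overall: 26.7% above the mean and 13.3% below. The mean of a standard normal variable above zero is 0.798. The shift in standardised GA 34 gain among observed women is 0.798 × (0.733 − 0.867)/(2 × 0.8) = −0.0665. In kg of final gain this is 4 × r × 0.0665, which is 0.21 kg at r = 0.8 and 0.24 kg at r = 0.9. The arm's mean is too low by that amount, or 0.21/2.8 = 8% to 0.24/2.8 = 9% of the target difference.

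**The case against.** The strongest reply is that the definition matches the stated target, gain from the onset of pregnancy to birth, and that the SAP nowhere says women are excluded. Both points stand. A reader might infer that GWG is wrongly defined because weight gain is a trajectory. The SAP does not support that: gain at birth is a coherent outcome, and the fix keeps it. Exclusion is an inference from linear regression plus silence, though it is the only reading the text supports.

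The size is also open to challenge. The 20% is overall loss to follow-up taken from similar trials, not a rate of missing birth-day weights, and many women lost to follow-up would have no GA 34 weight either. The 7–10% gain is therefore a best case, which is why the half case is shown. The bias scenario is hypothetical; nothing in the SAP suggests such a pattern. The pandemic warning does not single out birth-day weights, and the GA 28 and GA 34 weights could be lost as well.

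There is partial mitigation. Section 5 offers planned visits after withdrawal, reports losses by group and visit, and compares completers with non-completers at baseline. The COVID-19 sensitivity analysis is not restricted to the primary outcome. None of these handles a missing birth-day weight in the GWG comparison.

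Nor can the matter simply be left to the protocol. The SAP itself fixes the outcome, the model, the scope of imputation and the missing-data rule, and those provisions leave GWG uncovered.

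**Conclusion.** The point holds as a modest weakness in the analysis of a tested secondary outcome. Weights scheduled for GWG have no stated use, no rule covers a missing birth-day weight, and no sensitivity analysis examines it. Under the assumptions above, the avoidable loss is about 4–5% of the standard error if half of the affected women have a GA 34 weight and 7–10% if all do. One-sided selective missingness could shift an arm's mean by about 0.2 kg.

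Two stronger readings go too far. A reader might infer that the GWG comparison is underpowered; on the SAP's own figures, 33/66 is still met at 20% loss and complete-case power for 2.8 kg is 0.924. A reader might also infer that the GWG result will be biased; the SAP shows only that selective missingness would go unchecked, and the illustrated shift is small beside 2.8 kg. The case for change rests on using data already scheduled under a weaker missingness assumption.

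**What to change.** Keep GWG at birth as the outcome and state in Section 6 how the GA 28 and GA 34 weights deal with missing birth-day weights. Either route would do:

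- a likelihood-based repeated-measures model of gain from preconception at GA 28, GA 34 and delivery, with group-by-visit and baseline-activity-by-visit terms and an unstructured covariance, reporting the group contrasts at delivery; or
- an extension of the planned mice imputation to GWG, with the GA 28 and GA 34 weights added as predictors.

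Report the complete-case regression alongside.

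The cost is SAP wording and one standard analysis on weights already scheduled; no new measurement is needed. The downside is reliance on missing-at-random given the earlier weights. That is weaker than what the complete-case regression assumes, but it does not correct missingness driven by events after GA 34, such as a transfer or complicated delivery not foreshadowed by earlier weights. Under the repeated-measures model, women with no preconception weight stay excluded.
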